## **PROTOCOL SYNOPSIS**

TITLE	Evaluation of the impact of fascial closure technique on post- operative pain in patients undergoing Pfannenstiel incision for Caesarean Section: A Randomised Trial
SPONSOR	DAN Women and Babies Unit, Sunnybrook Health Sciences Centre
FUNDING	DAN Women and Babies Unit, Sunnybrook Health Sciences Centre
ORGANISATION	
NUMBER OF SITES	1
RATIONALE	Caesarean sections are the most commonly performed surgical procedure throughout the world. Within the Canadian population, approximately one-third of all deliveries occur via Caesarean section. Chronic pain post-operatively has been identified as an issue that a large proportion of patients suffer with. As a result, a variety of surgical techniques have been undertaken, with some being compared to ascertain the reason for this chronic pain. One method which has been observed is related to the fascial layer and associated pain related to this layer. Whilst the abdominal fascia plays an integral role in ensuring the abdominal contents remain in situ. A variety of methods have been employed and studied to ensure the integrity of the fascial layer to reduce the risk of dehiscence, but no studies undertaken to date have evaluated the method of fascial closure and their effect on post-operative pain.
STUDY DESIGN	Randomised, double-blind, three-arm trial
PRIMARY OBJECTIVES	1. Analgesia use
	2. Pain score between three groups
NUMBER OF SUBJECTS	350
SUBJECT SELECTION	Inclusion Criteria:
	- Women aged 18-60 years
	- Women with singleton pregnancy
	
 
Patient undergoing elective lower segment Caesarean section via a Pfannenstiel Incision
 

	- Use of Regional Anaesthesia (epidural or spinal anaesthesia)
	Exclusion Criteria:
	- Multiple pregnancy
	
 
Patient undergoing non-elective Caesarean section
 

	- Caesarean section through midline laparotomy incision
	
 
Patients undergoing Caesarean section under General Anaesthesia
 

	- History of chronic pain
	
 
History of chronic pain
 
History of post-operative complications (haematoma, abscess,
 

	- History of post-operative complications (naematoma, abscess, dehiscence, re-operation)

	· · · · · · · · · · · · · · · · · · ·									
ARMS AND	Participants will be blinded to which method of fascial closure will									
INTERVENTIONS	be undertaken at the time of their surgery.									
	1. Single suture, knot above rectus fascia									
	2. Two sutures, knots above rectus fascia									
	3. Two sutures, buried knots below rectus fascia									
DURATION OF SUBJECT	Subjects will be enrolled in the study for 10 weeks.									
PARTICIPATION AND	Screening: 1 day									
DURATION OF STUDY	Treatment: 1-2 days (subjects will be admitted to hospital)									
	Follow-up: 10 weeks									
	The total duration of subject recruitment time is 6 months, with									
	subsequent follow-up over a 10-week period after initial									
	recruitment.									
EFFICACY										
EVALUATIONS										
PRIMARY ENDPOINT	1. Analgesia use in first 72-hour period post-operatively.									
	2. Pain score questionnaire results over 10-week post-operative									
	period.									
STATISTICS										
Primary Analysis Plan	Statistical analysis will be undertaken using IMB ® SPSS ® Statistical									
	Software ver. 26 to undertake a two-sided T-test comparing group									
	1 vs. 2 and group 1 vs. 3 to assess for statistical significance in									
	analgesia use and pain scores.									
Rationale for Number	Based on a power of 80% at an alpha of 0.05, we estimate a 15%									
of Subjects	reduction in pain scores. As a result, we require a total of 255									
	subjects in this study. Given an estimated drop-out rate of 35%, we									
	aim to recruit a total of 350 participants.									
	In addition, sub-group analysis will be undertaken comparing pain									
	scores between primary and repeat Caesarean sections. Based on									
	the same power of 80% at an alpha of 0.05, with an estimation of a									
	15% difference in pain scores, we require a total of 140 subjects for									
	this sub-group analysis.									
L										

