## **3** STUDY OBJECTIVES

### 3.1 Primary Objectives

The primary objective in this study is to evaluate post-operative pain in patients undergoing elective lower segment caesarean sections via a Pfannenstiel incision. The intervention in question relates specifically to the method by which the rectus fascia is closed. Participants will fill in a pain questionnaire over a period of 10 weeks at set intervals to ascertain their level of pain on visual analogue scores and requirements for analgesia.

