#### 7.3 Data collection method

Participants will be randomised to one of the three groups and will be provided a participant identification number on the day of their surgical procedure after consenting to proceed with the study. Subsequent to this, a chart review will be used to gather demographic information on participants, including age, gravida and para status, number of previous Caesarean sections, medical and surgical history, medication list, body mass index, and any obstetrical complications during the pregnancy. Participant's e-mails will be collected and saved in a separate document to maintain confidentiality.

Subsequent to this, participants will be e-mailed a link at each given time parameter to fill in their questionnaires which is a modified MD Anderson Brief Pain Inventory as a secure Google Docs Form (post-operative day #1 and 2, and at 2, 6 and 10 weeks post-operatively). As the participant's only identification is their participant identification number, this maintains participant confidentiality.

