#### **APPENDIX C: Pain Survey Questionnaire**

Fascial Closure – Follow-up Study Questionnaire:

Your personal ID: \_\_\_\_\_

Throughout our lives, most of us have had pain from time to time (such as minor headaches, sprains, and toothaches). Have you had pain other than these everyday kinds of pain today?

- □ Yes
- □ **No**

Did you take pain medication in the last 7 days?

[figure not shown]
- □ Yes
- □ No

I feel I have some form of pain now that requires medication each and every day.

- □ Yes
- □ **No**

If your answers to the above 3 questions were all "No", please stop here and go to the end of the questionnaire and please press "Submit". If any of the above 3 answers were "Yes", please continue.

On the diagram below, please identify the area that hurts the most.

Where would you identify this pain?

- □ Superficial (closer to the skin)
- □ Deep

Please rate the number that describes your pain level at its WORST in the last 24 hours

0 1 2 3 4 5 6 7 8 9 10

Protocol Number: FAS-101ConfidentialVersion 1.0Version Date: 25 November 2020																	
No Pin												Wo	orst pai	n you	can im	agine	
Please rate the number that describes your pain level at its LEAST in the last 24 hours.																	
	0	1	2	3	4	5	6	7	8	9	10						
No Pin												Wo	orst pai	n you	can im	agine	
Please rate the number that describes your pain level on AVERAGE.																	
	0	1	2	3	4	5	6	7	8	9	10						
No Pin												Wo	orst pai	n you	can im	agine	
Please	rate	• the	nun e	nbe	r tha	at de	scrit	nes v	our	pair	n leve	I RIGHT					
. ieuse	0	1	2	3	4	5	6	7	8	9	10			•			
No Pin			_						-	-		Wo	orst pai	n you	can im	agine	
What k	ind	of t	hings	s ma	ike y	/our	pain	fee	l be	tteri	? (i.e.	heat, n	nedicin	ie, rest	:, mass	age)?	
							·				`			,		0 /	
What k	ind	s of	thing	gs m	ake	you	r pai	n wo	orse	(i.e.	walki	ing, sta	inding,	lifting	)?		
14/1											· c.						
What t	reat	mei	nts o	r me	eaic	atior	is ar	e yo	u re	ceiv	ing to	r pain?					
													_				
In the l	ast	24 h	ours	, ho	w m	nuch	relie	ef ha	ve	bain	treatr	nents o	or med	icatio	ns prov	ided? Pl	lease identify the
percen									-						•		,
-			0%	10	)%	20%	5 3	0%	40	%	50%	60%	70%	80%	90%	100%	
No Reli	ief			C	ב					]							Complete relief
For eac				owii	ng w	ords	s, ple	ease	che	ck a	ll adje	ctives	that ap	ply to	your p	ain.	
	Ac	hing	5														
Burning																	
Dull																	
Exhausting																	
□ Gnawing																	
□ Miserable																	

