
 
Nagging
 
																	
□ Numb																	
		-	•														
			-														
		ooti	-														
		abbi	-														
	Tender																

Protocol Number: FAS-101 Confidential Version 1.0 Version Date: 25 November 2020 Throbbing Tiring Unbearable In the last 24 hours, how much has your pain interfered with your general activity? 6 7 Does not interfere **Completely interferes** In the last 24 hours, how much has your pain interfered with your mood? Does not interfere Completely interferes In the last 24 hours, how much has your pain interfered with your walking ability? Does not interfere **Completely interferes** In the last 24 hours, how much has your pain interfered with your normal work (includes both work outside the home and housework)? Does not interfere **Completely interferes** In the last 24 hours, how much has your pain interfered with your relations with other people? 2 3 6 7 Does not interfere Completely interferes In the last 24 hours, how much has your pain interfered with your sleep? Does not interfere П **Completely interferes** In the last 24 hours, how much has your pain interfered with your enjoyment of life? Does not interfere **Completely interferes** I prefer to take my pain medication: On a regular basis Only when necessary Do not take pain medicine I take my pain medicine (in a 24 hour period): Not every day 1 to 2 times per day 3 to 4 times per day 5 to 6 times per day 

more than 6 times per day

Do you feel you need a stronger type of pain medication?

- □ Yes
- □ No
- □ Uncertain

Other methods I use to relieve my pain include: (Please check all that apply)

- □ Warm compresses
- □ Cold compresses
- Relaxation techniques
- Distraction
- □ Biofeedback
- □ Hypnosis
- Other: \_\_\_\_\_

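### As described, data collection does not measure the first primary endpoint, 72-hour analgesia use, over its whole window or as an amount

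*Combined protocol and SAP*

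**What the plan says.** - **Endpoint.** The Protocol Synopsis lists "Analgesia use in first 72-hour period post-operatively" as the first of two primary endpoints. The second is the pain questionnaire results over 10 weeks.
- **Analysis.** The Synopsis plans two-sided t-tests of group "1 vs. 2 and group 1 vs. 3 to assess for statistical significance in" analgesia use and pain scores. Section 10.2 repeats the t-test. Neither place gives a unit, a list of drugs or a summary measure for analgesia use.
- **Source.** Section 3.1 has participants complete a questionnaire to establish "their level of pain on visual analogue scores and requirements for analgesia".
- **Timing.** Section 7.3 e-mails that form on "post-operative day #1 and 2, and at 2, 6 and 10 weeks post-operatively".
- **Chart review.** Section 7.3 says "a chart review will be used to gather demographic information on participants". Its list, like that in section 10.1, consists of demographic, history and pregnancy items. It includes a medication list but not doses given after surgery.
- **Form content.** Appendix C asks "Did you take pain medication in the last 7 days" (yes/no), whether daily medication is needed (yes/no), which treatments are being received (free text), and one frequency item, "I take my pain medicine (in a 24 hour period", with bands up to "more than 6 times per day".
- **Setting.** The Synopsis gives a hospital stay of 1-2 days. Section 6 describes two scheduled oral drugs and an as-needed opioid, all three continued at home.

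**The concern.** A t-test needs one number per woman. The endpoint covers hours 0-72, yet the described collection has no form between post-operative day 2 and week 2 and never asks how much of any drug was taken. If the plan is followed as written, one of the two primary endpoints has no defined numeric variable and no recorded amounts after discharge. Inpatient doses could be abstracted from hospital records later, but home doses that nobody recorded could not be recovered. A null result on analgesia would then be hard to interpret, because women with different opioid use can give the same answer. Section 1 motivates the trial partly by the wish to reduce opioid requirements, and section 2.1 hypothesises a reduction in analgesia use.

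**Working it through.** The plan gives no calculated figure for this endpoint. Its 85 per arm is linked to a 15% reduction in pain scores. The check is therefore of coverage and content.

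**1. Hours reached by the forms.** Inputs are the schedule (section 7.3) and the 24-hour reference of the frequency item (Appendix C), read generously as the 24 hours before completion.
- Two forms × 24 h = 48 h at most. 72 − 48 = 24 h unmeasured, and 24/72 = 33%.
- Forms at hours 24 and 48 miss hours 48-72. Forms at hours 48 and 72 miss hours 0-24. Changing the timing moves the gap but does not close it.
- If days are calendar days and surgery is at 08:00-16:00 (assumed), day 2 ends at hour 72 − 8 = 64 or 72 − 16 = 56. A form completed on day 2 then cannot reach hour 72.
- Week 2 is day 14. Its longest look-back is 7 days, and 14 − 7 = day 7 = hour 168. It recovers nothing from hours 0-72.
- The 7-day item on the day 1 and day 2 forms gives only yes/no and reaches back before surgery.

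**2. Hours reached by inpatient records, if they were used.** With a stay of 1-2 days counted from surgery, the time at home is 72 − 48 = 24 h to 72 − 24 = 48 h, or 33-67% of the window.

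**3. Amount.** Inputs are the section 6 frequencies. One scheduled drug every 6 h is 4 a day and the other every 12 h is 2 a day, so there are 6 scheduled administrations, or 4 occasions if taken together. The opioid every 4 h is at most 6 doses a day, at 1-2 mg each. What a band means depends on what a woman counts (scheduled drugs fully taken in the last three rows):

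| What she counts | Band | As-needed doses a day | mg a day |
|---|---|---|---|
| As-needed doses only | 1-2 | 1-2 | 1-4 |
| | 3-4 | 3-4 | 3-8 |
| | 5-6 | 5-6 | 5-12 |
| Occasions, opioid taken separately | 5-6 | 1-2 | 1-4 |
| | over 6 | 3-6 | 3-12 |
| Occasions, opioid taken with scheduled drugs | 3-4 | 0-4 | 0-8 |
| All administrations | over 6 | 1-6 (6 + 1 = 7 to 6 + 6 = 12) | 1-12 |

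The form does not say which count is wanted and does not separate drugs. On the first reading the bands keep most of the ordering of women by use. On the last, every opioid user falls in one band. On none of them does the form give a 72-hour total.

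**The case against.** **The source is inferred.** The Synopsis attaches the questionnaire to the second endpoint, not the first, and section 3.1 does not mention 72 hours. Hospital records may have been intended. Section 11.1 requires source documents covering all pertinent data, the case report form is not shown, and the consent form is not in the text available for review. This stands as a limit: a diary or record review described elsewhere cannot be ruled out. It does not remove the point, because the documents name no other source and inpatient records end at discharge.

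**The SAP is still to come.** Section 10 defers detail to a later SAP. That document can define a variable, but it cannot create home doses that no form asked for.

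**Stronger readings.** A reader might infer that the endpoint cannot be analysed at all. The documents do not support that, because the bands and free text on days 1 and 2 allow a crude comparison. Inpatient records to discharge plus a form answered exactly at hour 72 could even touch the whole window, though the time at home would be covered only in bands.

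A reader might also infer a large loss of power. A simulation (85 per arm, assumed mean of 1-3 as-needed doses a day, between-woman gamma variance 0.25-1.0, 30% cut, bands scored as integers over days 1-2) put the cost of banding against exact 48-hour counts at about 0.02-0.05 if women report only as-needed doses. It was 0.14-0.44 if they count every administration. The dose mean, spread and cut are not in the documents. Full scheduled dosing on day 1 is also doubtful, since section 6 starts oral drugs only as the regional block recedes. The spread is the reason to quote no single loss.

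**Conclusion.** The point holds in this form: as described, the first primary endpoint is not measured over its stated window or as an amount. The frequency item leaves at least 24 of 72 hours (33%) uncovered, and no item asks dose or tablet count. Inpatient records, if used, would leave 24-48 hours to self-report. This rests on reading the frequency item as the previous 24 hours, counting the stay from surgery, and taking section 3.1 as the named source. It is more than missing detail, because following the schedule exactly still leaves part of the window unmeasured and the home doses cannot be recovered later. The pain-score endpoint, on which the trial was sized, is not affected by this gap. The plan should be changed before enrolment, or at once for participants still to come.

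**What to change.** 1. Add one e-mailed form at or after hour 72.
2. On the day 1, 2 and 3 forms, ask the number and strength of tablets of each prescribed analgesic taken since the last form. Place these items outside the skip rule that ends Appendix C after three negative answers.
3. Name the inpatient medication administration record as the source until discharge.
4. Pre-specify one numeric variable for hours 0-72, for example cumulative as-needed opioid in mg, and report use of each drug by arm.
5. If no day-3 contact is added, restate the window as 48 hours, time the day-2 form at or after hour 48, and keep the count items.

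The cost is one extra e-mail, a few form items and record extraction for up to 350 women. Over 48 hours that is at most 6 × 2 × 350 = 4,200 as-needed entries, and as many again if scheduled doses are extracted. The downside is that counts after discharge remain self-reported. No change to the analgesic regimen is proposed.

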## 1 BACKGROUND

Caesarean sections (CS) are the most commonly performed surgical procedure worldwide, with approximately one-third of all births occurring via Caesarean section in developed nations,(1-3) and over of 40% of deliveries in some nation such as Brazil(4). Specifically in the United States of America, this equates to nearly 1.3 million deliveries in 2016(4, 5). Given the difficulties associated with women undergoing a CS, coupled with expectation of recovering from a large surgical procedure whilst caring for a newborn present new challenges to the mother and her family.

Opioid analgesia is a common staple for post-surgical analgesia to aid in recovery. Unfortunately, due to the increase in Caesarean Section rates(1-3), there is more reliance on opioids to manage pain(6-9). This unfortunately is wrought with difficulties given the side-effect profile of opioid analgesics as well as their addictive potential(7). As a result, the reliance on alternative measures including surgical technique to minimise opioid requirements is an area of clinical research which requires further development(6, 9).

Anaesthetic technique and post-operative pain management play an integral role in postoperative pain. Another avenue which has been explored relates specifically to surgical techniques(2, 3, 5, 10-12). Studies have evaluated the type of incision(2, 3), method of skin closure(5), and closure of the peritoneum and its impact on post-operative pain(1). Specific to closure of the rectus fascia, Kahkhaie et al. evaluated the type of suture material used during Caesarean section and found their impact on post-operative pain(10). Finally, Trimbos et al. evaluated methods of fascial closure following midline laparotomy(12). Whilst these studies outline multiple surgical techniques and have shown impact on the risk of developing CPSP, no studies were found which directly compared the technique by which the fascia is reapproximated at the time of CS via a Pfannenstiel incision.

The purpose of this protocol is to outline our study evaluating three methods of closure of the rectus fascia and their effect on post-operative pain in patients undergoing lower segment Caesarean sections (LSCS) via a Pfannenstiel incision in a Canadian tertiary care obstetrical unit.

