- 3) The final method again involves two separate #1 Polysorb™ absorbable sutures (Covidien™). Both leafs of the rectus fascia are grasped with the Bonney forceps and the suture is placed behind the angle of the incision ensuring that the entire knot of the suture is below the rectus fascia. Subsequent to this, the suture is run in a continuous fashion to reapproximate the fascia until reaching the contralateral rectus abdominus muscle. Subsequently, a second #1 Polysorb™ suture is tied behind the contralateral angle in the same fashion and the remainder of the rectus fascia is reapproximated in a continuous fashion until both sutures are met, whereupon they are tied together.

The remainder of the procedure is completed whereupon the subcutaneous layer is inspected for haemostasis which is achieved using the electrocautery and is reapproximated if >2cm thickness with an absorbable suture. Subsequent to this, the skin is reapproximated using a 3-0 Caprosyn® (polyglytone\*6211) suture (CovidienTM) in a subcuticular fashion.

As a means of enhancing analgesia, our centre utilises epidural morphine standard as part of their regional anaesthesia for Caesarean Sections, this utilises a single-dose of 0.15mg morphine for spinal regional anaesthesia or a single-dose of 3mg morphine for epidural regional anaesthesia. Upon completion of the procedure, the patient receives one dose of diclofenac 100mg perrectum and is initiated on oral analgesia as regional anaesthesia wears off. The patient receives a standard analgesia regimen including Tylenol 1g orally every 6 hours, Naproxen 500mg orally every 12 hours, and hydromorphone 1-2mg orally every 4 hours as required for breakthrough

pain. They are subsequently discharged home with a prescription of these three medications for a short course.

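### Primary endpoint 1, analgesia use to 72 hours, names no drug or unit, and the questionnaire that is to measure it cannot separate as-required hydromorphone from scheduled analgesics

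*Combined protocol and SAP*

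**What the plan says.** The Synopsis lists two primary endpoints, the first being "Analgesia use in first 72-hour period post-operatively". No section says which drugs count, in what unit, how different opioids would be combined, or where the data come from. Section 3.1 says that the questionnaire will establish both pain level and analgesic requirements. Section 10.2 plans two-sided t-tests, and Section 10 leaves further detail to a SAP still to be written.

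Section 6 describes the oral drugs that every woman receives. Two are scheduled: "Tylenol 1g orally every 6 hours, Naproxen 500mg orally every 12 hours". One is not: "hydromorphone 1-2mg orally every 4 hours as required for breakthrough" pain. There is also a single rectal dose of diclofenac and a single neuraxial dose of morphine. All three oral drugs continue on prescription after discharge.

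The Appendix C item on frequency of use begins "I take my pain medicine (in a 24 hour period" and offers five bands: not every day, 1 to 2, 3 to 4, 5 to 6, and more than 6 times per day. It names no drug and asks for no dose. Section 7.3 sends the form on days 1 and 2 and at weeks 2, 6 and 10. The Synopsis gives the hospital phase as "Treatment: 1-2 days (subjects will be admitted to hospital").

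**The concern.** Of the oral drugs in the regimen, only hydromorphone is prescribed to follow the woman's pain. The endpoint does not single it out, and neither does the instrument that the protocol names for measuring analgesic requirements. If the plan is followed as written, the main record of analgesia use is a band that the schedule largely determines.

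Two women with quite different needs for breakthrough opioid can give the same answer, in any arm. A null result on this endpoint would then say little about whether closure technique changes the need for pain-driven analgesia. A SAP written later cannot recover drug-specific doses that were never collected.

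**Working it through.** **Inputs from the documents.** Acetaminophen every 6 h, naproxen every 12 h, hydromorphone 1-2 mg at most every 4 h (Section 6); window 72 h and stay 1-2 days (Synopsis); 85 per arm, 80% power, two-sided alpha 0.05 (Section 5.2); 15% reduction, stated for pain scores (Synopsis).

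**Step 1. What the schedule does to the frequency item.** Acetaminophen gives 24/6 = 4 times a day and naproxen 24/12 = 2. If both naproxen doses coincide with acetaminophen there are 4 medication times; if neither does, 4 + 2 = 6. The answer with no breakthrough pain is therefore the 3-to-4 or the 5-to-6 band. Now suppose a woman with 4 medication times takes hydromorphone with each acetaminophen dose, which the 4-hour minimum interval allows. She takes 4 hydromorphone doses a day, or 4 to 8 mg, and if she counts occasions her band does not change.

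**Step 2. Coverage of the window.** With a stay of 24-48 h, between 72 - 48 = 24 h and 72 - 24 = 48 h of the window falls at home. No form covers 48-72 h. The week 2 form looks back at most 7 days, to about day 14 - 7 = 7, so it does not reach the window.

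**Step 3. Make-up of a pooled dose count, if one were used.** Scheduled: 72/6 + 72/12 = 12 + 6 = 18 doses. As-required ceiling: 72/4 = 18 doses. Scheduled drugs, if fully taken, are at least 18/36 = 50% of the count. At an assumed mean of 6 hydromorphone doses they are 18/24 = 75%, and a 15% fall in hydromorphone (0.9 doses) is 0.9/24 = 3.75% of the total. At the ceiling it is 2.7/36 = 7.5%.

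**Step 4. The plan's own sample size.** No mean or SD is given, so 85 per arm can only be solved backwards. Detectable standardised difference = (1.960 + 0.842) × √(2/85) = 0.430. For a 15% reduction, SD/mean (CV) = 0.15/0.430 = 0.349. This CV belongs, by implication, to pain scores. Using it for hydromorphone doses is an assumption.

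**Step 5. Power for the t-test on a pooled count.** Power ≈ Φ(δ / [SD × √(2/85)] − 1.960). With mean 6 doses, δ = 0.15 × 6 = 0.9 and the hydromorphone SD is 0.349 × 6 = 2.09. If scheduled doses vary between women with SD s, independently of arm and of hydromorphone use, the pooled SD is √(2.09² + s²). For s = 0: 0.9/(2.09 × 0.153) = 2.80, and Φ(0.84) = 0.80. An exactly fixed 18 doses adds nothing to the SD, and a simulation of 4,000 trials gave 0.79 both with and without them. Power by assumption:

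| Mean doses | CV | s = 0 | s = 1 | s = 2 | s = 3 |
|---|---|---|---|---|---|
| 4 | 0.349 | 0.800 | 0.625 | 0.361 | 0.218 |
| 6 | 0.349 | 0.800 | 0.715 | 0.526 | 0.361 |
| 9 | 0.349 | 0.800 | 0.761 | 0.657 | 0.526 |
| 6 | 0.6 | 0.371 | 0.348 | 0.296 | 0.239 |
| 6 | 1.0 | 0.163 | 0.160 | 0.151 | 0.139 |

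For scale, missing 10% of 18 scheduled doses at random gives s = √(18 × 0.1 × 0.9) = 1.27. The simulated power was then 0.66 at mean 6 and CV 0.349.

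**The case against.** The best defence is that the scheduled drugs are the same in every arm. A constant added to both sides leaves the mean difference, the SD and the p-value unchanged. That is correct. A reader might infer that the fixed doses by themselves hide a real difference from the t-test, and they do not. They only make the difference a smaller percentage of the total. Nor can the 15% be held against total doses: the Synopsis states it for pain scores, Section 10.2 does not name the outcome, and no section sets a target for analgesia use.

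Nor does the protocol say that doses will be summed across drugs. An opioid-only or drug-by-drug analysis would fit its wording, and Appendix C has an open question on current treatments that could identify drugs, though not amounts. This limits Steps 3 and 5 to what would happen under pooling. It does not rescue the frequency item, which pools by its wording.

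A reader might also take opioid reduction to be the trial's purpose, since Section 1 speaks of "surgical technique to minimise opioid requirements". That passage is motivation. The stated purpose in the same section is the effect of closure technique on post-operative pain, and the hypothesis in Section 2.1 refers to analgesia requirements generally.

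Finally, scheduled intake may not be fixed in practice. At home women may skip doses or take them according to pain, and Appendix C allows such answers. Step 1 therefore applies to a woman who keeps to the schedule. Variation unrelated to pain is what costs power; if intake partly follows pain, some of that variation carries signal and Step 5 overstates the loss.

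**Conclusion.** The point holds in this form: endpoint 1 is undefined by drug and unit, and the questionnaire that is to measure it records all pain medicine together in bands that the schedule fills to 4-6 times a day. This is more than detail left for the SAP, because the data needed to separate as-required opioid would not be collected by the forms as written.

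The size is uncertain. The loss from banding was not quantified. For a pooled count, power falls from 80% to between 71.5% and 36.1% under the central assumptions, and hardly at all if hydromorphone use is very variable, where power is low to begin with (37% at CV 0.6 and 16% at CV 1.0, even for hydromorphone alone). The mean, the CV, the 15% effect on doses and the variation in scheduled intake are all assumptions. Separating the drugs makes the endpoint interpretable; it does not guarantee adequate power.

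**What to change.** Before data collection:

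- Define primary endpoint 1 as cumulative as-required opioid taken over 0-72 hours, in mg oral hydromorphone, with any other as-required opioid converted by a fixed table.
- Take inpatient doses from the hospital chart.
- On the early forms, replace the banded item with the amount of hydromorphone, or other as-needed opioid, taken since the last form (since surgery for the first).
- Add one short e-mailed form at 72 hours, since days 1 and 2 do not cover 48-72 hours. Bands on those two days could not yield milligrams when each dose is 1-2 mg.
- Report scheduled acetaminophen and naproxen separately, as adherence.

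The cost is the endpoint wording, one reworded item, extraction of chart doses and one short extra form. Scheduled non-opioid use becomes a secondary description. The analgesic regimen, visits and sample size are unchanged.
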